## 6.1 Production, Packaging, and Labeling

Both the MVA-BN-Brachyury and FPV-Brachyury bulk drug substances are produced at Bavarian Nordic A/S, Denmark. The final drug product is filled, formulated and labeled at Bavarian Nordic A/S, Denmark.

Address: Bavarian Nordic A/S

The packages and vials of liquid frozen MVA-BN-Brachyury and FPV-Brachyury vaccines are labeled with United States Investigational New Drug Application labels.

## 6.2 Shipment, Storage, and Handling

Usage of the investigational medicinal product (IMP) is only allowed upon final approval of all shipment relevant paperwork by Bavarian Nordic or its authorized designee. Only patients enrolled in the trial may receive IMP.

Supplies of MVA-BN-Brachyury and FPV-Brachyury will be shipped temperature controlled and monitored, to the clinical trial site from a central United States depot. Once at the site, the package should be handed over to personnel in charge of IMP preparation (e.g., the pharmacist). Site personnel are responsible for proper storage of IMP and upon receipt. All IMP must be stored in a secure environmentally controlled and monitored area in accordance with the labelled storage conditions with access limited to the investigator and authorized site staff.

Both the MVA-BN-Brachyury and the FPV-Brachyury vaccines must be shipped to the site and stored at a temperature of  $-20^{\circ}\text{C} \pm 5^{\circ}\text{C}$  or  $-80^{\circ}\text{C} \pm 10^{\circ}\text{C}$  avoiding direct light. A vial must not be re-frozen once it has been thawed.

Additional details on the shipment, storage and handling of the MVA-BN-Brachyury and FPV-Brachyury can be found in a separate pharmacy manual supplied to each clinical trial site.

### **6.3 Preparation, Administration, and Dosage**

Detailed trial-specific instructions on the preparation and administration of MVA-BN-Brachyury and FPV-Brachyury are provided in a separate pharmacy manual supplied to each clinical trial site.

#### **6.3.1 Radiotherapy**

Radiotherapy must meet minimum requirements to achieve a reasonably effective dose. The minimum expected dose to provide biologic rationale for the combination is 8Gy in 1 fraction for each target lesion. Documentation by a radiation oncologist of an equivalent or higher biologic dose is adequate to meet requirements for eligibility and treatment on protocol. A patient who does not cross this threshold is not considered to have received treatment per protocol and will not be assessed for response per RECIST 1.1 criteria for the primary analysis/objective.

##### **6.3.1.1 Minimum Radiation Treatment Requirements**

1. The minimum radiotherapy dose required for biologic effect is established based on the preclinical data as 8 Gy in 1 fraction. The following are examples of calculations that are equivalent doses biologically to 8 Gy in 1 fraction. For each patient, the treating radiologist should calculate the biologic equivalent dose to ensure that the minimum biologic dose is reached. Any dose at least meeting this equivalence is potentially eligible, given that the treating radiation oncologist does not believe the dose will cause harm to normal surrounding structures.
  - a. 8 Gy in 1 fraction (8 Gy / fraction)
  - b. 20 Gy in 5 fractions (4 Gy per fractions; minimally 12 Gy received)
  - c. 30 Gy in 10 fractions (3 Gy/fraction; minimally 15 Gy received)
  - d. 40 Gy in 20 fractions (2 Gy / fraction; minimally 20 Gy received)
2. Normal tissue surrounding the tumor must be protected by the standards of the treating institution for that organ system. For example, if a given institution requires that no normal spinal cord tissue receives more than a maximum point dose of 30 Gy (using 6 Gy / fraction bioequivalence), the treating radiation oncologist must comply with institutional standards when calculating the dose to the tumor center. This capability to meet requirements 1 and 2 must be determined for the target lesion prior to enrollment on trial.

### **6.3.1.2 Guidelines for Radiotherapy for Definitive/Unresected Chordoma Treated with Curative Intent:**

To allow for standardization of radiation treatments, the following recommendations are provided:

For treatment of unresected primary or recurrent chordomas with gross measurable disease, the following treatment is recommended based on a series of experience ([DeLaney et al., 2009](#)) ([Park et al., 2006](#)) ([Chen et al., 2013](#)) ([Kabolizadeh et al., 2017](#)) showing high local control with these treatment volumes and doses.

**Gross Target Volume (GTV):** The GTV is any gross tumor(s) visualized on the treatment planning CT scan and or MRI.

**CTV1 (Clinical Target Volume 1)** is the GTV and tumor bed plus all tissues suspected on invasion by tumor on a subclinical basis. This includes 1.5 to 3 cm margin for areas of extraosseous extension into muscular compartments such as gluteus muscles, piriformis muscles, erector spinae muscles or along neurovascular bundles such as sciatic nerve; the entire involved vertebra; a vertebral level above and below the maximal extent of intraspinal canal involvement; and 0.5-1.0 cm in bone or abutting soft tissue confined by a fascial, cartilaginous, bone, or disc space barrier, bowel, lung interface. Generally the CTV1 dose level should be reduced to 45 to 46.80 GyRBE (gray relative biological effectiveness) in patients with these co-morbidities: active autoimmune disease, insulin requiring diabetes.

CTV1 will receive a dose of 50.4 Gy (or GyE with Relative Biological Effectiveness of 1.1 to 1 proton: photons if given with protons)

CTV2 will consist of the GTV plus any tumor bed with a 0.5 cm margin and should receive an additional dose of up to 27 Gy in 1.8 Gy per fraction or equivalent.

**Planned Target Value (PTV):** The clinical target volumes will be expanded (generally by 2-5 mm based on institutional practices) to generate a PTV to account for the intrafraction motion anticipated for the target volume in the immobilized patient during the treatment delivery. The prescribed dose is specified to the isodose contour which encompasses the planning target volumes on each proton field; this must be >95%.

### **6.3.1.3 Treatment Planning**

Treatment planning is to be performed using 3D CT based planning systems. For patients with lesions of the spine above the level of the conus, a lumbar instillation of iodinated contrast material is recommended for the radiation planning CT scan to fully visualize the spinal cord unless medically contraindicated or MRI for treatment planning/fusion can be acquired in the immobilized treatment position. Image fusion with the diagnostic or a dedicated treatment planning MRI scan should be performed to optimize target definition(s).

### 6.3.1.4 Immobilization

The patient will be in customized head or body immobilization. The treatment planning CT is to be performed with the patient in this mold; contrast will be employed unless there is a history of contrast allergy. In these sensitive patients, there will have been obtained a diagnostic MRI with gadolinium to aid in the designation of tumor involved tissue(s).

### 6.3.1.5 Normal Tissue Constraints

Dose volume histograms (DVH) for target volumes and selected normal tissues will be generated. Normal tissues evaluated will include (depending upon anatomic level) spinal cord, cauda equina, and sacral nerves.

DVHs to be generated, by tumor site:

**Table 8 Normal Tissue Radiation Dose Constraints**

STRUCTURE	DOSE SURFACE	DOSE CENTER	DOSE CONTRA	LENGTH, VOLUME, AREA
Cervical Cord	67 GyRBE	55 GyRBE	50 GyRBE	5 cm
Thoracic/Lumbar Cord	63 GyRBE	54 GyRBE	50 GyRBE	5 cm
Cauda Equina	77.4 GyRBE*	70.2 GyRBE	70.2 GyRBE	*adjacent to tumor
Sacral Nerves	77.4 GyRBE*	77.4 GyRBE*	77.4 GyRBE*	*adjacent to tumor
Skin Over Spine	66 GyRBE			≤ 100 cm 

STRUCTURE	DOSE
Esophagus	< 1/3 < 65 GyRBE; 2/3 < 55 GyRBE; whole volume ≤45 GyRBE
Lungs	V20 GyRBE < 1/3
Heart	1/3 ≤ 60 GyRBE; 2/3 ≤ 45 GyRBE; entire volume ≤ 30 GyRBE
Small Bowel	57.6 GyRBE for < 50% circumference over length < 10 cm; otherwise 50.4 GyRBE for volumes ≤ 300 mL
Colon	≤ 66 GyRBE to < 1/3 of circumference over length of 5 cm
Rectum	Posterior 1/3 ≤ 77.4 GyRBE over 5 cm and ≤ 70.2 GyRBE over 8 cm
Kidneys	At least 2/3 of one kidney to receive < 20 GyRBE
Liver	≤ 50% volume > 25 GyRBE; ≤ 40% volume ≥ 30 GyRBE

GyRBE = gray relative biological effectiveness; cm = centimeter; cm^2 = square centimeter; mL = milliliter

Source: data provided by Massachusetts General Hospital

## Quality Assurance

### Dose Specification

A minimal of 95% of the prescription dose should be prescribed to a minimum of 95% of target volume at each dose level. Deviations and reasons for deviation should be recorded.

Radiation guidelines for treatment of metastases or recurrences with palliative intent: Palliative radiation given to metastases or recurrences at primary site may vary across institution. Details of dose, fractionation, and technique should be recorded. A minimum of 8 Gy x 1 (or biologic equivalent as described in [Section 6.3.1.1](#)) should be used for palliation. Stereotactic body radiotherapy (SBRT) should follow standard guidelines for safety.

Radiation to secondary non-target sites: May be allowed if demonstrates progression and will be evaluated for RECIST 1.1 response.

## 6.4 Accountability and Disposal

Used (if allowed by institutional policy) and unused vials of all IMP need to be retained in a place with limited access until appropriate drug accountability has been performed. Drug accountability must be documented whenever the IMP is either prepared or administered.

Bavarian Nordic will provide a Drug Accountability Log for recording receipt, dispensation, and destruction of IMP (see Pharmacy Manual). Alternative systems used to track drug accountability are acceptable for use in the trial provided the aforementioned items are adequately captured and records are available for review during scheduled monitoring visits to the site.

After drug accountability has been performed, used and unused vials should either be returned to the designated drug depot, a vendor selected by Bavarian Nordic, or discarded according to local regulations.

Destruction or return of IMP must be agreed upon with Bavarian Nordic and appropriately documented. Documentation should be reviewed and signed off by the pharmacist and Clinical Research Associate assigned to monitor the site.

Sites are responsible for the proper destruction and disposal of used needles and syringes and this should be done according to local regulations. If local disposal is not possible, used clinical supplies may be returned to the designated drug depot or a vendor selected by Bavarian Nordic after prior consultation with Bavarian Nordic.

## **7 Blood Collection for Correlative Biomarker Studies (Exploratory)**

### **7.1 Collection of Blood Samples**

A total of 274mL blood will be taken for exploratory analyses from each patient during the trial. Blood samples will be collected from all enrolled patients as described in [Section 1.5](#).

1. Six green top sodium heparin tubes (10 mL volume) will be taken for PBMC preparation.
2. One SST tube (8.5 mL volume) for serum preparation.

### **7.2 Sample Analysis**

Testing will be performed at Bavarian Nordic (Munich).

#### **7.2.1 Analyses of PBMCs:**

1. Pre- and post-baseline PBMCs, separated by Ficoll-Hypaque density gradient separation, will be analyzed for antigen-specific immune responses. PBMCs will be stimulated in vitro with overlapping 15-mer peptide pools of control peptides and tumor antigen associated peptides e.g. Brachyury.
2. Post-stimulation analyses of CD4 and CD8 T cells will involve the production of activation associated cytokines e.g. IFN- $\gamma$ .
3. PBMCs from selected patients may be analyzed for numbers/percentages in standard immune cell types (e.g. CD4 and CD8 T cells, natural killer [NK] cells, regulatory T cells, myeloid-derived suppressor cells, and dendritic cells) and their activation status.
4. HLA typing will be performed on the most abundant PBMC sample for each patient.

#### **7.2.2 Analyses of Serum**

1. Sera will be analyzed pre- and post-baseline for changes in the amount of soluble factors e.g. sCD27, sCD40 ligand
2. Selected patients may be analyzed for antibodies to human tumor antigens e.g. Brachyury, carcinoembryonic antigen or MUC1.

#### **7.2.3 Collection, Processing, and Testing of Biomarker Samples**

A United States-based central laboratory will be responsible for distribution of sample collection kits as well as for collecting, processing and storage of samples as well as for sample management.

Serum samples will be processed, aliquoted and interim-stored at the clinical sites and shipped to the central laboratory at the end of the collection phase.

[figure not shown]
Fresh Blood samples for PBMC purification have to be shipped priority overnight on the day of blood draw to the central laboratory for processing on the next day.

All samples and aliquots generated will contain labels having the clinical trial protocol and a unique sample identification number.

All samples will be pseudonymized, only the patient number will be provided by the clinical sites to the central laboratory.

Exploratory Biomarker analyses will be done at:

Bavarian Nordic GmbH

In addition, a Clinical Research Organization may be selected to perform specific analyses.

### **7.3 Future Use of Lab Specimens**

Specimens remaining after completion of all immunogenicity testing for the trial will be stored for future analysis supporting the licensure path of BN-Brachyury. Patients will be asked to consent to storage/future use of their samples and will be informed about data protection measures. Specimens will be stored in Bavarian Nordic's secured laboratory area or at an external storage facility in a coded, pseudonymized manner to ensure data protection.

## **8 Safety**

### **8.1 Definitions**

#### **8.1.1 Adverse Event**

An adverse event is defined as any reaction, side effect, or untoward event that occurs during the course of the clinical trial (starting with the signature of the informed consent form), whether or not the event is considered related to the treatment or clinically significant. For this trial, AEs will include events reported by the patient, as well as clinically significant abnormal findings on physical examination or laboratory evaluation. A new illness, symptom, sign or clinically significant laboratory abnormality or worsening of a pre-existing condition or abnormality is considered an AE. All AEs must be recorded on the AE case report form.

All AEs, including clinically significant abnormal findings on laboratory evaluations, regardless of severity, will be followed until satisfactory resolution. AEs should be reported up to 30 days following the last dose of trial drug.

An abnormal laboratory value will be considered an AE if the laboratory abnormality is characterized by any of the following:

- Results in discontinuation from the trial
- Is associated with clinical signs or symptoms
- Requires treatment or any other therapeutic intervention
- Is associated with death or another serious adverse event, including hospitalization.
- Is judged by the Investigator to be of significant clinical impact
- If any abnormal laboratory result is considered clinically significant, the investigator will provide details about the action taken with respect to the test drug and about the patient's outcome.

### **8.1.2 Suspected Adverse Reaction**

Suspected adverse reaction means any adverse event for which there is a reasonable possibility that the drug caused the adverse event. For the purposes of Investigational New Drug application safety reporting, 'reasonable possibility' means there is evidence to suggest a causal relationship between the drug and the adverse event. A suspected adverse reaction implies a lesser degree of certainty about causality than adverse reaction, which means any adverse event caused by a drug.

### **8.1.3 Unexpected Adverse Reaction**

An adverse event or suspected adverse reaction is considered "unexpected" if it is not listed in the investigator brochure or is not listed at the specificity or severity that has been observed; or, if an investigator brochure is not required or available, is not consistent with the risk information described in the general investigational plan or elsewhere in the current application.

"Unexpected", also refers to adverse events or suspected adverse reactions that are mentioned in the investigator brochure as occurring with a class of drugs or as anticipated from the pharmacological properties of the drug, but are not specifically mentioned as occurring with the particular drug under investigation.

### **8.1.4 Serious Adverse Event (SAE)**

An adverse event or suspected adverse reaction is considered serious if in the view of the investigator or the sponsor, it results in any of the following serious criteria:

- Death (with the exception of death due to progression of underlying malignancy).
- A life-threatening adverse drug experience (any adverse event or suspected adverse reaction that places the patient or patient, in the view of the investigator or sponsor, at immediate risk of death from the reaction as it occurred, i.e., it does not include a reaction that had it occurred in a more severe form, might have caused death).
- Inpatient hospitalization or prolongation of existing hospitalization, with the exception of the following

- Hospitalization for planned surgery or procedure.
- A visit to the emergency room or other hospital department < 24 hours and/or that does not result in admission.
- Persistent or significant incapacity or substantial disruption of the ability to conduct normal life functions.
- A congenital anomaly/birth defect.
- Important medical events that may not result in death, be life-threatening, or require hospitalization may be considered a serious adverse drug event when, based upon appropriate medical judgment, they may jeopardize the patient or patient and may require medical or surgical intervention to prevent one of the outcomes listed in this definition.
- Other Cancer (with the exception of non-melanoma skin cancer).
- Transmission of Infectious Agent (e.g. pathogenic or nonpathogenic) via the trial vaccine(s).
- Overdose (accidental or intentional administration of any dose of a product that is considered both excessive and medically important).
- In addition, any Adverse Event of Special Interest (AESI) will be reported in the same fashion as an SAE regardless if serious criteria have been met.

### **8.1.5 Adverse Event of Special Interest**

For the purposes of this trial any Immune-Mediated Adverse Event (i.e. auto-immune diseases and immune-mediated clinical syndromes) occurring since first exposure to MVA-BN-Brachyury, will be treated as an AESI.

So far, no signal has emerged from the diverse poxvirus constructs studied in the clinic, but the theoretical possibility exists that breaking the immune tolerance to self-antigens may induce autoimmune phenomena. This deserves close vigilance.

### **8.1.6 Unanticipated Problem**

Any incident, experience, or outcome that:

- Is unexpected in terms of nature, severity, or frequency in relation to
  - (a) the research risks that are described in the Institutional Review Board (IRB)-approved research protocol and informed consent document; Investigator's Brochure or other trial documents, and
  - (b) the characteristics of the patient population being studied; **AND**
- Is related or possibly related to participation in the research; **AND**

- Suggests that the research places patients or others at a *greater risk of harm* (including physical, psychological, economic, or social harm) than was previously known or recognized.

## 9 Assessments and Trial Procedures

### 9.1 Medical History

Clinically relevant Medical history occurring prior to signing of Informed Consent Form (ICF) should be collected. Special attention should be paid to any history of vaccine allergies. When reporting SAEs, medical history considered relevant to the reported SAE should be indicated within the SAE report. Additionally, any ongoing concomitant medications started prior to ICF signing should have the indication reported as medical history.

### 9.2 Prior and Concomitant Medication

All non-cancer treatment prior and concomitant medications taken in the 90 days prior to the screening visit will be captured. Prior cancer treatments will be captured indefinitely. In regards to SAE reporting: Any clinically relevant concomitant medication taken within 30 days prior to the onset of an SAE must be indicated as such within the SAE report. Any medications taken in response to the SAE are considered treatment medications, within the context of SAE reporting, and should also be indicated as such within the SAE report.

Anti-emetics and antidiarrheal agents may be administered as required, but are not anticipated to be needed and should not be used prophylactically. Selection of the specific antiemetic regimen is at the discretion of the treating physician. Antiemetic regimens should not include dexamethasone or other steroids.

Toxicities thought to be autoimmune related and attributable to vaccine would lead to discontinuation of vaccine and symptomatic treatment. This may also include the use of immune suppressive treatments such as glucocorticoids and replacement hormones if indicated.

Other supportive care with blood components, antibiotics, analgesics, general medical therapy, etc., will be delivered as required. Any patients taking antibiotics for any reason must complete that course of therapy and be free of evidence of further infection before receiving any dose of vaccine.

Live, attenuated vaccine including influenza vaccine (FluMist), are not allowed within 4 weeks of Day 1 and throughout the trial.

Symptomatic anemia should be treated with appropriate red blood cell or erythropoietin support.

Other investigational therapies will not be allowed while a patient participates in this trial.

No additional therapies, besides those dictated by the trial (vaccine and radiotherapy), to treat chordoma are allowed on trial. In the case of progression of a non-target lesion, local therapeutic interventions are allowed on protocol, including surgery or radiation. In these cases, the primary target lesion is still the only target to be used for assessment of efficacy. Interventions to other sites are allowed to provide treatment alternatives for patients while they remain on trial to evaluate the results of the experimental treatment.

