#### 4.2.5 Withdrawal from Vaccination

Patients will be withdrawn from vaccination if any of the following is true:

- Target lesion disease progression as determined by
  - Radiographic disease progression by standard RECIST 1.1
  - Symptomatic disease progression by symptoms with concurrent evidence of any tumor enlargement
  - NOTE: A patient may continue on trial, at the investigator's discretion, with progression if he/she is eligible for local intervention for a non-target lesion progression
  - NOTE: A patient may remain on trial after initial evidence of target lesion disease progression until a confirmatory scan has been performed due to tumor swelling that can occur with radiotherapy and/or immunotherapy
- Patient withdrawal of consent (must document patient rationale for withdrawal)
- Positive pregnancy test
- Intercurrent illness or medical circumstances. If at any time the constraints of this protocol are detrimental to the patient's health, the patient may be removed from protocol therapy. In this event, the reasons for withdrawal will be documented.
- Adverse events meeting the following criteria: Evidence of any  $\geq$  Grade 3 allergic and  $\geq$  Grade 3 autoimmune reaction(s) attributed to vaccine (**except** Grade 3 endocrine-related immune toxicity or Grade 3 endocrine-related immune toxicity that resolves to Grade  $\leq$  1 clinically within 7 days of initiating supportive therapy); or if  $>$  Grade 2 toxicity attributed to vaccine persists for  $>$  28 days, the patient will not receive further vaccine injections. Patients who come off treatment must be followed on trial until resolution of toxicity and until disease progression.

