### FPV-Brachyury

- FPV-Brachyury is a liquid-frozen, highly attenuated, live recombinant virus. It is administered as subcutaneous application.
- One FPV-Brachyury vial has a nominal virus titer of  $1 \times 10^9$  Inf.U in 0.5 mL of the drug product. The specific dose will be determined upon release testing of the drug product.
- For further details on the FPV-Brachyury vaccine, see current version of the Brachyury Investigator's Brochure.

No dose modifications will be allowed on this trial. Any patient who experiences a dose limiting toxicity or allergic or autoimmune toxicity as defined in [Section 4.2.5](#) will not receive any additional vaccinations.

[figure not shown]
If a scheduled dose of the vaccine is missed, the vaccine may be given within the treatment window specified in [Section 1.5](#). If the patient has a delay in vaccination not due to toxicity, the vaccine may be delayed for up to 42 days without removal of the patient from trial.

**Dosing Delay:** Patients should have resolution to  $\leq$  Grade 1 or return to baseline of all toxicities prior to the start of the next injection of the vaccine. If  $>$  Grade 2 toxicity attributed to vaccine persists for  $>$  28 days, the patient will not receive further vaccine injections and will be removed from vaccine therapy.

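### Section 9.2 discontinues vaccine for any vaccine-attributed autoimmune toxicity, while Section 4.2.5 starts at Grade 3 and exempts a Grade 3 endocrine category that it names twice

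*Protocol*

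**What the plan says.** Three places in the protocol bear on stopping vaccine for toxicity.

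- **Section 9.2 (Prior and Concomitant Medication):** "Toxicities thought to be autoimmune related and attributable to vaccine would lead to discontinuation of vaccine and symptomatic treatment". The next sentence adds: "This may also include the use of immune suppressive treatments such as glucocorticoids and replacement hormones if indicated". There is no grade threshold, no exception and no reference to Section 4.2.5.
- **Section 4.2.5 (Withdrawal from Vaccination):** withdrawal applies to allergic reactions of Grade 3 or higher and, at the same threshold, to "Grade 3 autoimmune reaction(s) attributed to vaccine". The exception in brackets covers "Grade 3 endocrine-related immune toxicity or Grade 3 endocrine-related immune toxicity that resolves to Grade" 1 or lower within 7 days of starting supportive therapy. A separate limb stops vaccine if a toxicity above "Grade 2 toxicity attributed to vaccine persists for" more than 28 days.
- **Section 6 (FPV-Brachyury):** "Any patient who experiences a dose limiting toxicity or allergic or autoimmune toxicity as defined in" Section 4.2.5 receives no more vaccine. The dosing-delay paragraph asks for resolution to Grade 1 or lower "or return to baseline of all toxicities prior to the start of the next injection of the vaccine". It then repeats the 28-day rule, after which "the patient will not receive further vaccine injections and will be removed from vaccine therapy".

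The evaluable analysis set (Protocol 10.4.1, SAP 3.2) requires, among other things, at least 3 of the 4 FPV-Brachyury boosters in the 14 weeks after radiation. Patients who do not meet the evaluable criteria are replaced, with stated exceptions.

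**The concern.** A site that follows Section 9.2 and a site that follows Section 4.2.5 would treat the same vaccine-attributed immune event differently. The conflict falls on the risk that the protocol itself singles out. Section 8.1.5 makes immune-mediated events adverse events of special interest and asks for close vigilance. Table 3 lists thyroid (4/6) among the normal tissues that express the target. Exclusion criterion 7 admits patients with clinically stable autoimmune endocrine disease. An endocrine immune event is therefore foreseeable, and it is the category that 4.2.5 exempts and 9.2 does not.

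The analysis is exposed as well. Stopping vaccine early enough takes a patient out of the primary population and can lead to replacement, in a design of 29 evaluable patients with a threshold of 4 responses. SAP 3.5.8.2 also tabulates adverse events leading to discontinuation, and treatment delay and discontinuation for immunotherapy toxicity. Those counts would partly reflect which section a site had read.

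**Working it through.** The documents give no figure to reproduce and no arithmetic is needed beyond a booster count. The check applies the printed wording to each type of vaccine-attributed toxicity and compares the outcomes.

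| Vaccine-attributed toxicity | Sections 4.2.5 and 6 | Section 9.2 | Result |
|---|---|---|---|
| Autoimmune, Grade 1 | No withdrawal, no hold | Discontinue | Conflict |
| Autoimmune, Grade 2 | No withdrawal; hold until Grade 1 or lower or baseline, then resume | Discontinue | Conflict |
| Endocrine immune, Grade 3, down to Grade 1 or lower within 7 days | Exempt on either limb; hold, then resume | Discontinue | Conflict |
| Endocrine immune, Grade 3, resolving after 7 but within 28 days | Exempt on the unconditional limb, not on the 7-day limb | Discontinue | Conflict on the unconditional limb; 4.2.5 itself unclear |
| Autoimmune non-endocrine, Grade 3 or higher; endocrine, Grade 4 | Withdraw | Discontinue | Agree |
| Allergic, Grade 3 or higher | Withdraw | Silent | No conflict |
| Any toxicity above Grade 2 for more than 28 days | Stop, same terms in both sections | Discontinue if autoimmune, otherwise silent | No conflict |
| Non-immune, Grade 3 or higher, resolving within 28 days | No adverse-event criterion met in 4.2.5; hold, then resume under Section 6 unless it counts as dose limiting | Silent | Ambiguous |

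**Is endocrine toxicity within Section 9.2?** Its management sentence names replacement hormones, so endocrine events appear to be included.

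**The exemption in 4.2.5.** Call the first limb A (Grade 3 endocrine immune toxicity) and the second limb B (the same toxicity, resolving to Grade 1 or lower within 7 days). Every event in B is also in A, so A or B equals A and the 7-day condition excludes nothing. Take a Grade 3 endocrine event lasting 20 days: it is exempt as printed, but not exempt if the 7-day condition was meant to bind. The text does not show which was intended.

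**Dose limiting toxicity.** Section 6 uses the term and points to 4.2.5, which does not contain it. Grade alone does not supply the meaning: Section 2.5.3 reports no dose limiting toxicities in the Phase 1 trial although one vaccine-related Grade 3 event occurred. If the cross-reference is meant to cover this term too, the two sections agree. If not, the trigger is undefined.

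**Link to the evaluable set.** The post-radiation boosters fall at 2, 6, 10 and 14 weeks, and 3 are needed, so 4 − 3 = 1 may be missed. A patient discontinued before the third of these has at most 2 and is outside the evaluable set. A patient held and resumed may still reach 3. Discontinuation after the third booster, and at any later 12-weekly dose, does not affect this criterion.

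**The case against.** The strongest reply is that sites have an obvious primary source. Section 4.2.5 is the section on withdrawal from vaccination, and Sections 4.2.6 and 6 both refer to it. The sentence in 9.2 sits in the concomitant-medication section and introduces permitted steroids and hormone replacement. That makes 4.2.5 the likelier rule in practice. It does not remove the conflict, because 9.2 states a consequence for vaccination with no qualifier and no reference to 4.2.5.

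Several stronger readings are tempting, and the documents do not support them:

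- A reader might infer that all three sections contradict one another. Section 6 defers to 4.2.5 and repeats its 28-day rule, so those two are not shown to conflict.
- A reader might infer that severe non-immune toxicity is also governed by contradictory rules. That case rests on an undefined term and is an ambiguity. Other controls exist: 4.2.5 allows removal for medical circumstances, and Sections 4.4 and 4.5 send unexpected Grade 3 or higher reactions possibly related to MVA-BN-Brachyury to the DSMB.
- A reader might infer that 4.2.5 lets vaccination carry on through an active Grade 2-3 event. The dosing-delay text in Section 6 holds the next injection until resolution to Grade 1 or lower or to baseline. The contrast is stop against hold and resume. Only at Grade 1, or where the event is already back at baseline, is it stop against continue.
- A reader might infer that 9.2 makes discontinuation permanent. That is the natural reading, but the section does not say so.

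The effect on the analysis is possible, not shown. Section 8.1.5 reports no autoimmune signal so far, Section 2.5.6 reports no autoimmune events with PROSTVAC, and the SAP includes a sensitivity analysis on the full analysis set.

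**Conclusion.** The concern holds between Section 9.2 on one side and Section 4.2.5, with Section 6 following it, on the other. As printed, the outcomes differ for two classes of event: Grade 1-2 autoimmune toxicity, and Grade 3 endocrine immune toxicity resolving within 28 days. In addition, the exemption in 4.2.5 contains a 7-day condition with no effect, so its intended scope is unclear, and Section 6 relies on a term that 4.2.5 does not define.

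The size cannot be given as a number of patients, because the documents state no expected frequency for these events. What can be said is that the choice of section can decide whether a patient reaches 3 of 4 post-radiation boosters, and so whether that patient counts in the primary analysis or is replaced.

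The conclusion assumes that endocrine immune toxicity falls under the autoimmune wording of 9.2, which its mention of replacement hormones supports, and that the sentence in 9.2 is an instruction and not only background. Nothing here says which rule is clinically right. Because the passages give conflicting instructions on giving further vaccine after vaccine-attributed immune toxicity, they should be reconciled.

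**What to change.** 1. Reconcile Sections 9.2 and 4.2.5 into one discontinuation rule, stated once, and have Sections 6 and 9.2 refer to it without restating it. The rule should settle the grade at which a vaccine-attributed autoimmune toxicity stops vaccine and whether any category is exempt.
2. Correct the duplicated exemption in 4.2.5 so that each limb states what was intended and the role of the 7-day condition is clear.
3. Clarify how dose limiting toxicity in Section 6 relates to 4.2.5.

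The sponsor's clinical and safety leads must decide the content of each item. The cost is amendment wording and a notice to sites. No new procedures, visits or patients are needed.
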